Patients who are lost to follow-up or withdrawn prior to the 2 month follow-up visit due to an RA or RV lead related complication will be analyzed as having experienced a complication at the date the complication occurred. Patients who withdraw for reasons unrelated to an RA or RV lead related complication will be censored at the date of withdrawal.

Analysis

The desired outcome is to reject both null hypotheses for the RA and RV endpoints. The RA and RV hypothesis will be tested separately. The null hypothesis for the RA or RV endpoints will be rejected at the 2.5% significance level if the 95% lower limit of a two-sided confidence interval for the freedom from RA or RV lead-related complications by 2 months is greater than 92%. The confidence

interval will be constructed using the log-log transformation of the event free estimate at 2 months.

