Patients who are lost to follow-up or withdrawn prior to the 12 month follow-up visit due to an RA or RV lead related complication will be analyzed as having experienced a complication at the date of the complication. Patients who withdraw for reasons unrelated to an RA or RV lead related complication will be censored at the date of withdrawal.

Analysis

The desired outcome is to reject both null hypotheses for the RA and RV endpoints. The RA and RV hypothesis will be tested separately. The null hypothesis for the RA or RV endpoints will be rejected at the 2.5% significance level if the 95% lower limit of a two-sided confidence interval for the freedom from RA or RV lead-related complications between 2 months and 12 months is greater than 95%. The confidence interval will be constructed using the log-log transformation of the event free estimate at 12 months.

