4.2.4.1 Freedom from system-related complications

The hypothesis is formally expressed as:

H_0 : Freedom from system related complications through the 12 month visit $\leq 80\%$

H_a : Freedom from system related complications through the 12 month visit $> 80\%$

The desired outcome is to reject the null hypotheses. The null hypothesis will be rejected at the 5% significance level if the 95% lower confidence limit for the freedom from system related complications at 12 months is greater than 85%.

Simulation was used to calculate the sample size requirements for testing the Kaplan-Meier estimated survival probability for the freedom-from-complication endpoint. The expected proportion of patients free from system related complications at 12 months is 0.975 (95% CI: 0.924, 0.992) using data from the VICTORY pulse generator IDE study (G050191). For a study size of 800 patients and a Type 1 error rate for the hypothesis test of $\alpha = 0.05$ for a one-sided test, the power is greater than 98%.

Patient Group

All patients that have had an attempted implant or a successful implant of an Accent MRI system will be included in this endpoint.

Patients who are lost to follow-up or withdrawn prior to the 12 month follow-up visit due to a system related complication will be analyzed as having experienced a complication at the date of withdrawal. Patients who withdraw for reasons unrelated to a system related complication will be censored at the date of withdrawal.

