4.4.4 Complete System Explants

If the patient has the entire Accent MRI system removed at any time during the study, and the patient will not receive a replacement Accent MRI system, follow the patient for 30 days, and withdraw the patient from the study. Complete and submit the forms listed below to St. Jude Medical. A system revision form is not required to be submitted.

- Withdrawal Form
- Product Out of Service Form
- Adverse Event Form, if applicable
- Death Form, if applicable

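### Section 4.2.4.1 dates a complication that ends in withdrawal at the withdrawal date, unlike the lead endpoints, so one event can carry two dates and, if 12 months means day 365, a late one can be missed (minor)

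*Combined protocol and SAP*

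**What the plan says.** - **Section 4.2.4.1 (secondary endpoint), Patient Group.** The rule covers "Patients who are lost to follow-up or withdrawn prior to the 12 month follow-up visit due to a system related complication". It places the event at withdrawal: those who leave "due to a system related complication will be analyzed as having experienced a complication at the date of withdrawal". Unrelated withdrawals are censored on the day they leave.
- **Sections 4.2.1.1 and 4.2.1.2 (acute lead endpoints).** A patient who leaves because of a lead complication "will be analyzed as having experienced a complication at the date the complication occurred".
- **Sections 4.2.1.3 and 4.2.1.4 (chronic lead endpoints, also to 12 months).** Such a patient "will be analyzed as having experienced a complication at the date of the complication".
- **Section 4.4.4.** After complete explant with no replacement system, sites are to "follow the patient for 30 days, and withdraw the patient from the study".
- **Cut-off in 4.2.4.1.** The hypotheses run through the 12 month visit, but the null is rejected "if the 95% lower confidence limit for the freedom from system related complications at 12 months is greater than 85" per cent. Kaplan-Meier is named in the sample-size paragraph of that section.
- **Table 3.** The 12 month visit has a window of 60 days either side.

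The plan gives no reason for treating the system endpoint differently.

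**The concern.** The patient-group paragraphs in 4.2.1 and 4.2.4.1 are built the same way and differ in the date given to the event. The leads are part of the system. A lead complication that is also adjudicated as system-related, and that ends participation, would have one date in the primary analysis and a later one in the secondary analysis.

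The gap has a fixed minimum in one route. If the complication is dated no later than the explant, section 4.4.4 puts withdrawal at least 30 days after it. In a time-to-event estimate read at a fixed day, an event moved past that day disappears from the estimate. The patients concerned are those whose complication was serious enough to take them out of the study. The endpoint is also the first in the fixed testing sequence of section 4.2.4, so it gates the two capture-threshold secondaries.

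**Working it through.** **1. The plan's own figure.** Inputs from 4.2.4.1 are N = 800, expected rate 0.975, one-sided alpha 0.05 and stated power above 98%. The exact binomial rule succeeds with at most 141 failures against 80%, or at most 103 against 85%. The expected number of failures is 800 × 0.025 = 20. Power is about 1.000 in both cases, so the statement reproduces. (The section states a null of 80% and a rejection limit of 85%. That is a separate matter, and both were checked.)

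**2. Can an event cross the cut-off?** Take 12 months as day 365. The visit may then fall between day 305 and day 425.

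- Explant without replacement on day 345, withdrawal on day 345 + 30 = 375.
- Day 375 precedes a visit allowed up to day 425, so the rule in 4.2.4.1 applies.
- Read at day 365, the patient is at risk and event-free, and the event is left out.
- Read at the 12 month visit, the event counts, but 30 days late and in a later risk set.

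With a 30-day lag, only explants after day 335 can cross.

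**3. What share of events falls in the last 30 days?**

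- *Even spread (assumption):* 30/365 = 8.2%.
- *Registry timing from 4.2.1.* RV complications are 1 − 0.993 = 0.007 in months 0–2 and 1 − 0.998 = 0.002 in months 2–12. RA complications are 0.005 and 0.004. The share in the first two months is 0.007/0.009 = 78% (RV) and 0.005/0.009 = 56% (RA). Spreading the remainder evenly over ten months, the last month holds (0.002/10)/0.009 = 2.2% (RV) and (0.004/10)/0.009 = 4.4% (RA).

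These are lead rates, not system rates, but they are the only timing data in the plan.

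**4. Expected number of events moved past day 365, 30-day lag.** The documents do not say how many of the 20 expected events end in withdrawal, so a range is shown.

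| Events ending in withdrawal | RV timing | RA timing | Even spread |
|---|---|---|---|
| 2 of 20 | 0.04 | 0.09 | 0.16 |
| 5 of 20 | 0.11 | 0.22 | 0.41 |
| 20 of 20 | 0.44 | 0.89 | 1.64 |

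For the middle row, dividing by 800 gives 0.014, 0.028 and 0.05 percentage points on the estimate.

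Longer lags are assumptions. With 5 withdrawals, 60 days gives 0.22, 0.44 and 0.82 events, and 90 days gives 0.33, 0.67 and 1.23.

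**5. Effect on the test.** Kaplan-Meier was simulated under both dating rules, read at day 365, with evenly spread events and 10% unrelated dropout. Log-log limits were used, borrowed from the primary endpoints because 4.2.4.1 names no interval method.

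- *True rate 0.975:* a quarter of complications ending in withdrawal and a 30-day lag moves 0.4 events and raises the estimate by about 0.05 percentage points. Power is about 100% under both rules.
- *True rate 0.85:* the chance of clearing the 85% limit goes from about 5% to about 6% if 10% of complications end in withdrawal (30-day lag). It reaches about 22% only if every complication does.

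**The case against.** The case against giving this much weight has several parts, and most of it stands.

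- **A reader might infer that late events are certainly lost.** The documents do not settle that. The hypotheses run through the 12 month visit, and the rule covers only withdrawals before that visit. If the visit is the cut-off, nothing is dropped.
- **A reader might infer that the shift always favours the device.** It does not. An event dated later but still inside the year falls in an equal or smaller risk set, so its drop in the Kaplan-Meier curve is equal or slightly larger. Only an event that crosses the cut-off helps.
- **A reader might spread events evenly over the year.** The plan's registry rates put 56% to 78% of first-year lead complications in the first two months, which roughly halves the effect or better.
- **The affected group is narrow.** Revisions with repositioning or replacement keep the patient in the study (4.4.5.1). An unsuccessful implant leads to withdrawal after 30 days (4.4.3), far from month 12. The fixed lag near month 12 comes from complete explant without replacement.
- **Loss to follow-up might seem to lag further.** Section 9.0 requires two calls and a certified letter but gives no timing. It does not say whether the recorded date is last contact or declaration.

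What the objection does not remove is the difference between 4.2.4.1 and 4.2.1. The tipping-point analysis in 4.2.4.4 does not cover it either. That analysis replaces missing data, and a patient whose event is dated after day 365 is observed and event-free at the cut-off.

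**Conclusion.** The inconsistency is real and the dating rule in 4.2.4.1 is wrong as written, but the severity is minor. Under the visit reading, only event times and risk sets are wrong. Under the day-365 reading, complications in about the last month before month 12 can be left out, in the device's favour. The size is about 0.1 to 0.2 events on the plan's registry timing, or about 0.4 with even spread. This rests on 20 expected events, an assumed 5 ending in withdrawal and a 30-day lag.

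The success rule tolerates 103 failures even against 85%, and 20 are expected, so neither the decision at the planned rate nor the stated power is touched. The 22% false-success figure should not be read as a realistic risk. It needs every complication to end in withdrawal, which the retention rule in 4.4.5.1 makes implausible.

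**What to change.** In 4.2.4.1, Patient Group:

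1. For withdrawals and losses due to a system-related complication, replace the withdrawal date with the date on which the complication occurred, as in 4.2.1.1 and 4.2.1.2.
2. Keep the withdrawal date for censoring patients who leave for unrelated reasons.
3. State whether 12 months means day 365 or the 12 month visit, and use that wording in both the hypotheses and the rejection rule.

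The cost is one phrase and one clarifying sentence. Sample size and power do not change. The Adverse Event form's fields are not shown, but the lead endpoints already require the complication date, so it should be available.

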4.2.4.2 Bipolar atrial capture threshold at the MRI visit

The hypothesis is formally expressed as:

H₀: The proportion of patients with atrial capture threshold $\leq 2.0V$ at MRI visit is $\leq 85\%$

H_a: The proportion of patients with atrial capture threshold is $\leq 2.0V$ at MRI visit $> 85\%$

The proportion of patients with atrial capture threshold $\leq 2.0V$ at the MRI visit endpoint will be evaluated using a one-sided z-test, with variance calculated using the OPC of 85% at the $\alpha = 2.5\%$ level. The desired outcome is to reject the null hypothesis.

Patient Group

All patients implanted with the Tendril MRI™ lead with pre-MRI testing atrial capture threshold measurements at the MRI visit.

4.2.4.3 Bipolar ventricular capture threshold at the MRI visit

The hypothesis is formally expressed as:

H₀: The proportion of patients with ventricular capture threshold $\leq 2.0V$ at MRI visit is $\leq 85\%$

H_a: The proportion of patients with ventricular capture threshold $\leq 2.0V$ at MRI visit is $> 85\%$

The proportion of patients with ventricular capture threshold $\leq 2.0V$ at MRI visit endpoint will be evaluated using a one-sided z-test with variance calculated using the OPC of 85% at the $\alpha = 2.5\%$ level. The desired outcome is to reject the null hypothesis.

Patient Group

All patients implanted with the Tendril MRI™ lead with pre-MRI ventricular capture threshold measurements at the MRI visit.

4.2.4.4 Additional Secondary Endpoint Analyses

As supporting analyses for each of the three secondary endpoints, a tipping point analysis will be provided. In sequential fashion, each missing data point will be replaced by a “failure” after which the analysis will be re-run. This continues until either all missing data has been replaced with a “failure” or the test becomes non-significant (i.e.

the interpretation of the results changes). The proportion of missing data that would need to be a failure in order to change the analysis results will be reported and discussed.

4.2.5 Sub-group Analyses

Gender Analysis

The primary and secondary endpoints will be re-analyzed comparing the estimates for males and females. All relevant summary statistics will be reported.

Additionally, for the primary endpoints of freedom from RV/RA lead related complications in both the acute and chronic timeframes, a Kaplan-Meier analysis comparing freedom from lead complications between males and females will be provided. Note that with the large sample size associated with these endpoints, clinically irrelevant differences may be detected. This same type of analysis will also be done on the endpoint of freedom from MRI scan related complications.

All comparisons of gender will be done at the 0.15 level of significance.

4.2.6 Additional Data

- Ability to identify radiopaque identification marker on the pacemaker and lead through X-ray review by a cardiologist and radiologist
- Adverse Events – system, lead, and implant procedure related events (not including the primary safety endpoint)
- Atrial and ventricular bipolar capture thresholds immediately after MRI scan
- Atrial and ventricular unipolar capture thresholds before and after the MRI scan
- Atrial and ventricular bipolar lead impedance through the 1 month post MRI visit
- Atrial and ventricular bipolar sensing thresholds immediately after MRI scan
- Cardiac medications
- Challenges and lessons learned in communication between the MRI/Radiology and Cardiology teams

- Demographics: gender, age, ethnicity, race, cardiac disease history, arrhythmia history, indication for pacemaker implant, history of smoking, etc.
- Inadequate equipment availability during MRI scan
- Incidence of aberrant or undesirable behavior of the device while in the MRI mode.
- Incidence of MRI related arrhythmias and asystole
- Lead handling characteristics
- Loss or lapses in patient monitoring during the MRI scan
- Mortality
- MRI Activator performance and usability
- MRI image qualitative analysis; St. Jude Medical will provide data on the image quality/presence of artifact for the first 20 MRI scans performed. Each participating site will be asked to submit the first five MRI scans performed (up to 5 scans maximum) until 20 total scans have been submitted.
- Number of non-study related MRI scans
- Preliminary study phase small cohort - St. Jude Medical will summarize the adverse event data on the first 44 patients who complete the one month post MRI scan (29 MRI, 15 Control). This summary will be provided to the FDA.

4.2.7 Definitions to be used in the MRI study

Abnormal Lead Pacing Impedance: Measured pacing impedances with values $\leq 200 \Omega$ or $\geq 2000 \Omega$

Adverse Event: Any unfavorable clinical event which impacts, or has the potential to impact the health or safety of a patient caused by or associated with a study device or intervention. Adverse events are classified as complications or observations.

Complication: An adverse event caused by or associated with the study device, system component(s), and or procedure that requires invasive intervention (e.g. lead dislodgment requiring repositioning).

Cardiac Tamponade: Confirmed or suspected accumulation of fluid in the pericardial space

Cardiac Perforation: An excursion of the lead through the cardiac muscle. Signs and symptoms of a perforation by an intra-cardiac lead

may include radiographic evidence of excursion of the lead into the pericardial sac, abnormal echocardiography indicative of a perforation, the accumulation of fluid in the pericardium, cardiac tamponade, or patient symptoms such as chest pain and discomfort

Diaphragmatic/Phrenic Nerve Stimulation: Electrical activation of the diaphragm muscle by the device output pulse. The abrupt diaphragmatic contraction is noted clinically as hiccups associated with each pacing stimulus. The pacing stimulus may stimulate the diaphragm either directly or indirectly via the phrenic nerve.

Elevated Pacing Thresholds: Pacing thresholds > 2.0 V at 0.5 ms at implant. Following lead maturation at 6-8 weeks, an increase in pacing thresholds of 1.2 V at 0.5 ms or greater between visits. This definition is intended to serve as a guideline and it is understood that individual patients may have unique situations

Lead Dislodgement: The movement of a pacing lead from its originally implanted position resulting in elevated pacing thresholds or a decrease in sensing

Lead Fracture: A break in a conduction coil of a pacing or defibrillation lead typically evidenced by an increase in impedance, intermittent or complete loss of capture, intermittent or complete loss of sensing, noise on the intra-cardiac electrogram and visual signs of conductor coil fracture on x-ray

Lead Insulation Damage: A disruption to the integrity of the lead insulation without disruption of the conductor coil. An insulation break may be indicated by a drop in impedance, and can cause loss of capture or sensing problems

Loss of Capture: The inability of the device's output pulse to result in depolarization and contraction of the appropriate cardiac chamber. Causes include insufficient stimulus strength, separation of the electrode from the myocardium and placement of the stimulating electrode in contact with a non-responsive portion of the myocardium such as scar tissue. Delivery of an output pulse at a time when the myocardium is physiologically refractory is not loss of capture, since capture is not physiologically feasible

Loss of Sensing: A condition in which the pulse generator is unable to sense intrinsic cardiac signals

Observation: An adverse event caused by or associated with the study device, system component(s), and or procedure that does not requires invasive intervention (e.g. oversensing or loss of pacing capture requiring reprogramming).

Oversensing: The detection of inappropriate electrical signals by the pulse generator's sense amplifier. These signals, such as myopotentials, electromagnetic interference, T waves or crosstalk between atrial and ventricular channels, must be of sufficient duration to interfere with normal device function

Pneumothorax: An accumulation or suspected accumulation of air in the pleural cavity

Undersensing: The failure of the pulse generator to sense P or R waves, causing delivery of inappropriately timed, asynchronous or competitive output pulses. Undersensing can sometimes be corrected by programming the device to a more sensitive setting, i.e., decreasing the millivolt value

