4.2.2 Primary MRI Safety Endpoint: Freedom from MRI Scan-Related complications

An MRI Scan-Related complication is a complication caused by the interaction between the investigational pacing system and the MRI system that occurs during the MRI scan, including the time the patient is within the 5 Gauss line of the MRI system, up through the patient's 1 month post MRI visit. In addition, complications occurring due to the patient's MRI programming will be considered MRI scan related by the Clinical Events Committee (CEC).

The hypothesis is formally expressed as:

H_0 : Proportion of patients who are free from MRI scan-related complications between the MRI scan and one month post MRI visit $\leq 90\%$

H_a : Proportion of patients who are free from MRI-scan related complications between the MRI scan and one month post MRI visit $> 90\%$

The comparison criterion of 90% used for this objective denotes the minimum level for adequate safety following the MRI scan. Complications that can be attributed to the MRI scan are expected to occur within one month of the scan.¹⁹ Therefore, assessing this objective one month post-MRI scan will capture all MRI scan-related complications following the MRI scan procedure.

Sample Size

The expected proportion of patients free from complications under the null hypothesis is 0.90, and the Type 1 error rate is set at $\alpha = 0.025$ for the one-sided test. Assuming the portion of patients free from complications of 0.97, a sample size of 133 MRI patients provides a power level of 90% for this endpoint.

In another manufacturer's study involving an MRI conditional pacemaker, the complication free rate as observed to be 100%.¹⁹ Therefore, an assumption of 97% complications-free rate is assumed in the sample size calculation.

The objective will be evaluated using a one-sided z-test with variance of the test statistic based on the hypothesized value of 0.90 for the binomial proportion. The desired outcome is to reject the null hypothesis.

Patient Group

All patients implanted with the Accent MRI system who undergo an MRI scan and have completed their 1 month post MRI visit, or have an MRI-related complication before the end of the 1 month post MRI visit date will be included in the analysis of this endpoint.

Analysis

The analysis will be conducted on the per-protocol (PP) population. The per-protocol population includes patients who meet the following criteria:

- Successfully implanted with the Accent MRI system

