6.0 Adverse Events

A Clinical Events Committee (CEC) will review and adjudicate all Adverse Events. The CEC will base their final adjudication on the information provided on the case report forms, medical records, and their clinical knowledge and experience.

Adverse events (AEs) are any unfavorable clinical event which impacts, or has the potential to impact the health or safety of a patient caused by or associated with a study device or intervention. Adverse events will be classified as complications or observations.

Complications: Adverse events that require invasive intervention (e.g. lead dislodgment requiring repositioning).

Observations: Adverse events that can be managed without invasive intervention (e.g., oversensing or loss of pacing capture, which is remedied by reprogramming of the pacemaker).

Should an adverse event occur, complete an Adverse Event form and submit to St. Jude Medical. Report the adverse event to the IRB/MEC per the IRB/MEC policy. Any explanted devices or leads should be returned to St. Jude Medical for analysis.

Unavoidable AE: An unavoidable AE is defined as an adverse event related to the implant procedure or the MRI scan that is expected to occur for a projected duration in all patients. Unavoidable AEs are not reportable unless the condition worsens or continues beyond the time frame listed below. Unavoidable AEs, listed below, do not need to be reported if they are resolved within the time frame specified.

Table 6: Unavoidable AEs related to the Implant Procedure

Event	Time Frame post-Implant
Anesthesia related nausea/vomiting	<24 hours
Low-grade fever (<100 degree Fahrenheit fever or < 37.8 degree Celsius	< 48 hours
Pocket site/incision pain	< 72 hours
Mild to moderate bruising/ecchymosis at pocket site	< 72 hours
Sleep problems (insomnia)	< 72 hours
Back pain related to laying on the table	< 72 hours

Table 7: Unavoidable AEs related to the MRI Scan

Event	Time Frame post – MRI scan
Claustrophobia	During MRI scan
Mild diaphoresis	During and < 1 hour post MRI scan
Sensation of bodily warmth	During and < 1 hour post MRI scan
Hearing impairment	< 24 hours
Body stiffness related to immobility	< 48 hours

Definitions of AE relatedness:

Pacing system related: An AE that results from the presence or performance of the system under investigation.

Implant procedure related: An AE that occurs due to the implant procedure.

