MRI scan related: An AE which is caused by the interaction between the investigational pacing system and the MRI system that occurs during the MRI scan and includes the time the patient is within the 5 Gauss line of the MRI system and up through the patient’s 1 month post MRI scan follow up visit. In addition, AE’s occurring due to the patient’s MRI programming will be considered MRI scan related.

Potential MRI System Adverse Events:

- Lead electrode heating and tissue damage resulting in loss of sensing or capture or both
- Lead heating resulting in thrombus formation or embolism
- Device heating resulting in tissue damage in the implant pocket or patient discomfort or both
- Induced currents on leads resulting in continuous capture, VT/VF, hemodynamic collapse, or all three
- Damage to the device or leads causing:

- the system to fail to detect or treat irregular heartbeats
- the system to treat the patient's condition incorrectly
- Damage to the functionality or mechanical integrity of the device resulting in the inability of the device to communicate with the programmer
- Movement or vibration of the device or leads
- Lead dislodgment
- Competitive pacing and potential for VT/VF induction due to ambulatory asynchronous pacing in MRI mode
- Pulmonary Embolism

Potential Pacing System Adverse Events:

- Air embolism
- Body rejection phenomena
- Cardiac tamponade or perforation
- Hematoma, bleeding hematoma, seroma
- Formation of fibrotic tissue; local tissue reaction
- Inability to interrogate or program due to programmer or device malfunction
- Infection/erosion
- Interruption of desired pulse generator function due to electrical interference either electromyogenic or electromagnetic
- Loss of capture or sensing due to lead dislodgement or reaction at the electrode/tissue interface
- Loss of desired pacing and/or sensing due to lead displacement, body reaction at electrode interface, or lead malfunction (fracture or damage to insulation)
- Lead malfunction due to conductor fracture or insulation degradation
- Loss of normal pacemaker function due to battery failure or component malfunction
- Pacemaker migration, pocket erosion
- Pectoral muscle stimulation
- Phrenic nerve or diaphragmatic stimulation
- Pneumothorax/hemothorax
- Endocarditis
- Excessive bleeding
- Induced atrial or ventricular arrhythmias
- Myocardial irritability
- Pericardial effusion
- Pericardial rub
- Pulmonary edema
- Rise in threshold and exit block
- Valve damage

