8.0 Deaths

A Mortality Committee will review and classify all patient deaths. All patient deaths that occur during this investigation must be reported to St. Jude Medical as soon as possible. Notification of death should include a detailed statement of the pertinent events and be signed by the investigator in addition to the appropriate case report forms (Patient Death form, Patient Withdrawal form, and Product Out of Service form). It is the investigator's responsibility to notify the IRB/MEC per the IRB/MEC policy. Details of death and the following information, if available, should be provided in a letter to St. Jude Medical by the investigator summarizing the patient's course since enrollment in the study:

- Date and time of death
- Place death occurred (e.g. hospital, nursing home, patient's home)
- If death was witnessed
- Identification of the rhythm at the time of death, if known (include any available documentation)
- Cause of death
- Any other circumstances surrounding the death
- Approximate time interval to death from the initiating event.
- Autopsy report (if performed)
- Whether it was device and/or procedure related
- Whether it was related to the study
- Device configuration at the time of death

If any of the above information is not available, provide an explanation in the death narrative of what attempts (and how many) were made to obtain the information, and the outcome of those attempts. At a minimum, two (2) phone calls should be placed, followed by a certified letter, to the patient's next of kin. Provide clinical notes and witness statements. If possible, interrogate the pacemaker. Retrieve and print all episode diagnostics, IEGMs, and programmed parameters. If applicable, the pacemaker should then be programmed **OFF**.

Every attempt should be made to explant the pacemaker and/or leads intact. Any explanted devices or leads should be returned to St. Jude Medical for analysis

promptly. In the event that the device is not explanted, the above procedure must be followed to retrieve the data. The reason the pacemaker and/or lead(s) are not being returned to St. Jude Medical must be stated clearly on the case report form.

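### The primary MRI safety endpoint has no rule that counts scan-related deaths, or life-threatening scan events managed without invasive intervention, as failures

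*Combined protocol and SAP*

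**What the plan says.** **Event.** Section 4.2.2 builds the primary MRI safety event from the class of complications: it must be a complication, and it must arise from the interaction of the pacing and MRI systems (or from MRI programming) up to the 1-month visit. Section 4.2.7 defines a complication as "An adverse event caused by or associated with the study device, system component(s), and or procedure that requires invasive intervention", and 6.0 applies the same test. Section 4.2.2 states that assessment at one month "will capture all MRI scan-related complications following the MRI scan procedure".

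**The other class.** Adverse events have two classes only. The definitions of an observation differ:
- 4.2.7: "An adverse event caused by or associated with the study device, system component(s), and or procedure that does not requires invasive intervention"
- 6.0: "Observations: Adverse events that can be managed without invasive intervention"

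**Who is analysed.** The patient group in 4.2.2 is scanned patients who completed the 1-month visit or had an MRI-related complication before it. The per-protocol list in the same section requires 1-month data. A supporting analysis takes all scanned patients and replaces missing values by failures one at a time.

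**Foreseen hazards.** Among potential MRI system adverse events, 6.0 lists "Induced currents on leads resulting in continuous capture, VT/VF, hemodynamic collapse, or all three", as well as thrombus, embolism and pulmonary embolism. Section 4.4.6.6 defines sustained ventricular arrhythmia and asystole and sends both to an adverse event form. In 4.2.6, mortality and MRI-related arrhythmia and asystole are additional data without a hypothesis.

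**Deaths.** Section 8.0 says "A Mortality Committee will review and classify all patient deaths". No link to the endpoint in 4.2.2 is stated.

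**The concern.** The formal answer on acute scan safety is one proportion tested against 90%. The hazards for which the plan requires continuous monitoring and ACLS-capable staff can be serious or fatal without any invasive procedure. Under the definitions, such an event in a survivor is an observation and does not lower the proportion. A death before the 1-month visit with no adjudicated complication meets neither entry condition, so the worst outcome leaves the analysis. What the endpoint does respond to is mainly lead or device revision. Overall success requires this endpoint, so the gap reaches the main claim of the MRI phase.

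**Working it through.** **Inputs (4.2.2 and 4.1).** Null proportion p0 = 0.90; assumed proportion p1 = 0.97; one-sided alpha 0.025; power 90%; z-test with null variance; N = 133; MRI-phase enrolment up to 363.

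**1. Reproduce the plan's figure.** n = [(1.96·√(0.90·0.10) + 1.2816·√(0.97·0.03)) / 0.07]² = [(0.588 + 0.2186) / 0.07]² = 132.8, rounded up to 133. Power at 133 is 90.1%. The stated sample size is confirmed.

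**2. Pass mark.** The critical proportion is 0.90 + 1.96·√(0.09/n).
- n = 133: 0.951. 127/133 = 0.955 passes and 126/133 = 0.947 does not, so at most 6 failures.
- n = 363: 0.931, so at most 25 failures.

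**3. Trace two kinds of patient through the text.**
- *Survivor, event managed without invasive intervention, 1-month visit attended.* The event is not a complication. The patient is in the analysis set and counts as event-free.
- *Scan-related death before the visit, no adjudicated complication.* There is no completed visit and no counted complication, so the patient is in neither the patient group nor the per-protocol set.

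**4. Effect at the boundary.** Take 133 scanned patients, of whom 6 have invasive complications and 2 others have the event shown. z = (proportion − 0.90) / √(0.09/n).

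| The 2 further patients | As the plan reads | If counted as failures |
|---|---|---|
| Survivors of non-invasively treated VF | 127/133 = 0.955, z = 2.11, passes | 125/133 = 0.940, z = 1.53, fails |
| Deaths before the visit, no adjudicated complication | 125/131 = 0.954, z = 2.07, passes | 125/133 = 0.940, z = 1.53, fails |

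One further counted failure is enough: 126/133 gives z = 1.82, below 1.96.

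**5. The supporting analysis in the death example.** If the two deaths are handled as missing values, the first replacement gives 125/132 = 0.947, z = 0.0470/0.0261 = 1.80, which is not significant. The analysis would flag the problem, but its result is only reported and discussed. It cannot reach the survivors, whose data are not missing.

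**6. Power if the event is widened.** The documents give no rate for the added events. Assume the event-free rate falls from 0.97 by s, with 133 or 363 analysable patients:

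| s | n for 90% power | Power at 133 | Power at 363 |
|---|---|---|---|
| 0.5 points | 161 | 81% | >99.9% |
| 1 point | 196 | 70% | 99.8% |
| 2 points | 301 | 48% | 95% |
| 3 points | 498 | 30% | 77% |

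**The case against.** **The text is less firm than a strict reading.** Invasive intervention is undefined, and the CEC adjudicates every adverse event using its clinical knowledge and experience. It might class an external shock or a fatal arrest as a complication. A fatal event does not sit easily with 6.0, where an observation is something manageable without invasive intervention. This stands in part: the class of a fatal event is unresolved. But the primary endpoint then rests on discretion with no written rule.

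**A scan-caused death is not scored as free from complication.** A reader might infer that it is, because no invasive procedure took place. The entry conditions in 4.2.2 do not support this: without an adjudicated complication the patient is excluded, and the supporting analysis can set that patient to failure.

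**Fatal events can change the result.** A reader might infer that no number of them could. Exclusions shrink the denominator: with 25 failures, 338/363 gives z = 1.98 and passes, while dropping two deaths gives 336/361, z = 1.95, and fails.

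**Some hazards are covered.** Capture-threshold rise and sensing loss are primary efficacy endpoints in 4.2.3, and all must succeed. Asystole or embolism that does require invasive intervention counts as a complication.

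**Deaths and arrests are watched.** The CEC, the DSMB, the Mortality Committee and the rule on suspending the study all apply. These protect patients, but none has a stated role in deciding whether a death or arrest fails the 90% test.

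**The performance criterion was agreed with FDA, and the 97% assumption leans on an outside study whose event definition is not given.** This is a fair reason to leave the main definition largely in place and put the wider event in a supporting analysis.

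**Conclusion.** The concern holds in limited form. The primary MRI safety endpoint counts only scan-related events requiring an undefined invasive intervention. Survivors of serious scan events managed otherwise count as event-free, and early scan-related deaths without an adjudicated complication drop out.

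At the boundary of 6 invasive complications, two such patients decide the result: pass at z = 2.11 (survivors) or 2.07 (deaths), against fail at z = 1.53 if counted. The example is deliberately placed there. The plan's 97% assumption implies about 4 failures in 133 (0.03·133), and adding two to 4 would still pass. The documents give no rate for the uncounted events, so the chance of a changed conclusion cannot be stated.

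The conclusion rests on the ordinary reading that an external shock or drug treatment is not invasive intervention, which the plan does not say either way. The sample size of 133 is not in error.

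**What to change.** 1. **Deaths.** In 4.2.2, count as a failure any death between the scan and the 1-month visit that the CEC adjudicates as MRI scan-related, and keep that patient in the primary analysis set whether or not 1-month data exist.
2. **Definitions.** Define invasive intervention. Reconcile the patient group and per-protocol criteria in 4.2.2 with each other, and the definitions of complication and observation in 4.2.7 with those in 6.0, so that the class of a fatal event is settled.
3. **Wider supporting test.** Prespecify the same 90% test on a wider event: invasive complication, scan-related death, CEC-adjudicated scan-related sustained ventricular arrhythmia or asystole as defined in 4.4.6.6, or scan-related embolism. Report it beside the primary result.
4. **Lead safety.** Leave that definition unchanged, so that its registry-based assumptions still apply.

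The cost is a text change in 4.2.2, 4.2.7 and 6.0 and an instruction to the CEC. The events are already collected. The event-free rate may be slightly lower. With an assumed 1-point fall, power is about 70% at 133 and 99.8% at 363; the latter is the enrolment ceiling, so the analysable number may be smaller.
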